## Competence Assessment.

**Protocol:** After acquiring informed consent from the patient, 8 am fasting blood (7 tubes, 3 ml per tube = 21 ml total, **table 1**) will be collected to measure PA/A. Newly implanted patients with durable devices will have blood samples drawn on the day of discharge and outpatients will be asked to come into the heart failure clinic for a scheduled research visit. In-patients with acute CF pumps will be screened and enrolled 48 hours after device implantation. For enrolled in-patients with ongoing LLH, we will also draw serial blood tests (3 tubes, 3 ml per tube = 9mL) daily for up to three days to monitor PA/A studies, to assess ongoing effects of LLH on platelets.

Table 1: Hematologic studies for Aim 1	Durable CF Pump HM2 (n=50) and HM3 (n=75)		Acute CF Pump VA ECMO (n=45) and Impella (n=45)	
	LLH (HM2 n=15; HM3 n=15)	no LLH (HM2 n=35; HM3 n=60)	LLH (n=15 per device)	no LLH (n=30 per device)
PA/A studies (3 lightblue top tubes)				
-Aggregometry	x	x	x	x
-Flow Cytometry: P Selectin and GP 2b3a in platelet rich plasma				
Platelet cGMP measurement (1 blue top tube)	x	x	x	x
von Willebrand Factor electrophoresis and antigen/activity (2 lightblue top tubes)	x	x	x	x
ADAMTS-13 activity (1 lightblue top tubes)	x	x	x	x

**Study Procedures:** 1. PA/A studies: PA/A will be primarily measured by ex-vivo aggregometry (3 ml). In addition, secondary exploratory measures of PA/A will be assessed through flow cytometric detection of p-selectin and activated surface glycoprotein (GP) IIb/IIIa receptor. For platelet aggregometry and flow cytometry, studies will be promptly performed after specimen collection. Samples will be gently centrifuged to separate platelet-rich plasma (PRP) from white and red blood cells and platelet-poor plasma (PPP). PA/A will be assessed by a Multiple Analyzer (MA) after addition of an adenosine diphosphate (ADP) agonist to PRP. Although patients will be on aspirin, primary assessment of PA/A by aggregometry with ADP [ $>1\mu\text{m}$ ] in aspirin exposed platelets is preserved [26]. Aggregation is plotted against time. The maximum height of the curve represents the aggregation level, the slope is the reaction velocity, and the area under the curve (AUC) is calculated as the main aggregation measure, given in arbitrary units (AU) [12]. This ADP induced AUC will be the primary measure of PA/A in this proposal. P-selectin is a cell-adhesion glycoprotein which is present in the alpha granules of platelets. When platelets are activated, p-selectin localizes to the surface to mediate adhesion to other activated platelets, endothelial cells and leukocytes. Platelet membrane GPIIb/IIIa is a member of the integrin family of cell-membrane receptors that plays a key role in platelet aggregation and thrombus formation. Expression of activated GPIIb/IIIa receptors is exquisitely related to the PA/A. Both p-selectin and activated GP IIb/IIIa receptor in PRP will be measured through flow cytometry as previously described [17]. Prior to sample collection, 3 ml of blood will be wasted to eliminate the impact of venipuncture on PA/A. As the contemplated studies progress, the Platelet Activity State (PAS) Assay, which has been defined by our collaborating group by [name], will be added as an exploratory measure. The PAS assay evaluates mechanical shear-mediated platelet activation [27, 28].

2. Platelet cGMP: Whole-blood samples (3 ml) anticoagulated with citrate will be centrifuged to obtain PRP. Platelet cGMP will be quantified as described previously [35] by cGMP ELISA Kit (Cayman Chem., USA).

3. VWF studies: Standard gel electrophoresis will be conducted on plasma samples (3 ml). A

polyclonal rabbit antihuman antibody to vWF from Dako Inc. will be used to identify vWF multimers' bands which will be further quantified by densitometry. VWF activity will be measured from plasma (3ml) as the ratio of vWF collagen binding activity (measures binding of vWF to collagen as a function of the quantity of HMW multimers) to vWF antigen.

4. ADAMTS13 testing: Whole-blood samples (3 ml) will be centrifuged, and plasma will be removed. After repeat plasma centrifugation to remove platelet contamination, plasma specimens will be assessed for ADAMTS13 activity. This will be measured by a fluorescence resonance energy transfer (FRET)-based assay using a 73 amino-acid peptide (FRETS-VWF73) of von Willebrand factor (vWF) as a substrate [29].

*\*Plasma specimens for platelet cGMP, vWF and ADAMTS 13 activity studies will be frozen at -80°C and stored for analysis every week in batches during study period.*

5. LDH and plasma free hemoglobin are clinically measured daily on all inpatients and every 2 weeks in all outpatients with CF pumps by our institution's coagulation laboratory. As stated in the career and training plan, the candidate will be trained in the [name], [name], and [name] labs to become adept in platelet aggregometry, flow cytometry, the PAS assay and vWF and ADAMTS 13 activity studies. Then the proposed studies will be performed by the candidate at the home institution in [name] laboratory. In addition, a laboratory technician will be employed and trained to further assist with platelet aggregometry, flow cytometry (p-selection, GPIIb/IIIa receptor), platelet cGMP ELISA assays, VWF and ADAMTS13 activity studies.

**Statistical analysis, sample size calculations and timeline:** The primary measure for PA/A is ADP-induced AUC assessed by platelet aggregometry. ADP-induced AUC will be compared between the LLH and no LLH groups with an unpaired Student's t test. The null hypothesis is that there will be no difference in the PA/A between groups. A prior in-vitro study suggested that LLH increases PA/A by at least 30% as measured by aggregometry from  $20\pm 5$  to  $26\pm 4$  AU [12]. If this is the true population effect of LLH on PA/A in patients with CF pumps, with a minimum of 15 patients in each group per device we would achieve **90% power** to detect a significant difference in means with a two-sided alpha of 0.05. Since there will be fewer patients with LLH, we will recruit for both groups until we have enrolled 15 patients in the LLH group for each device. As device specific comparisons will be made, for durable CF pumps we estimate that we will have to screen 80 HM2 and 115 HM3 patients. We estimate that 35% of these patients will be excluded due to being on sildenafil, nitrates, active infection or withholding consent. This will leave 50 HM2 and 75 HM3 patients available for analysis. From historical data [30], we expect that approximately 30% of HM2 (n=15) patients and 20% of HM3 (n=15) will have LLH and the remainder will be in the no LLH group (35 HM2, 60 HM3). For acute CF pump support, we estimate that 90 VA ECMO and 90 Impella patients will need to be screened and after 50% exclusion, 45 VA ECMO and 45 Impella will be enrolled and available for analysis. Based on our preliminary data (**Figure 3C**) for VA ECMO and prior reports in Impella [31], we expect that at least 35% of patients for each acute CF pump (n=15 per device) will have LLH and the remainder will be in the no LLH group (n=30). At our institution there are 5 durable CF pumps implants (3 HM3 and HM2) and 6 acute support CF pumps (3 VA ECMO and 3 Impella) implanted every month. In addition, there are currently 125 stable outpatients with durable CF pumps (95 HM2 and 30 HM3) available for screening. Therefore, we estimate it would take 32 months to enroll and analyze the calculated number of patients for all devices (see timeline). For each device specific comparison, we will examine the confounding effects of age, sex, body mass index, race/ethnicity (such variables are known to effect

thrombosis during CF MCS) by comparing them between LLH and no LLH groups. If significant differences are found then adjusted multivariable models will be used to assess the independent association of LLH and PA/A. We will also assess if there are device differences by conducting a 1-way ANOVA test of the difference PA/A between LLH and no LLH amongst all 4 device groups and post-hoc comparisons if any significant difference is observed. Results from devices that do not show heterogeneity will be pooled to assess the association across device type. Similar to the device specific analysis noted above, confounders will also be examined, and if appropriate, adjusted for in this pooled sample. Lastly, we will compare for each device and in any pooled analysis, the association of LLH with potential mediators of PA/A including p-selectin, activated GP IIb/IIIa receptor, cGMP, vWF activity, UL/HMW multimers, ADAMTS 13 activity by unpaired Student's t tests.

**Anticipated results and experimental problems:** We expect that patients with LLH will have a significant increase in PA/A measured by ADP-induced AUC and associated higher p-selectin, activated IIb/IIIa receptor, lower levels of platelet cGMP, higher vWF activity, greater presence of UL/ HMW multimers, and lower ADAMTS 13 activity in comparison to those with no LLH. If an increase in PA/A is not observed at the selected LDH and PFHb thresholds, we may reanalyze the exposure impact of LLH as a continuous variable. If ADP induced PA/A is not observed then we may try other agonists to induce PA/A including TRAP, epinephrine, collagen, and arachidonic acid. As an alternative strategy, exogenous platelet activation on PRP will be assessed with PPP to evaluate for other hemolysate products that may impact PA/A. If cGMP is unchanged, then we will directly measuring NO bioavailability by Electron Paramagnetic Resonance (EPR) through FeDETC spin trapping methodology, which only captures the NO radical. If neither preceding platelet properties are changed then we will assess platelet agglutination, which is driven by vWF in a non-NO dependent mechanism. If changes in plasma UL/HMW multimers are not observed, we will further assess the ratio of HMW multimers to lower MW multimers. In addition, platelet-derived vWF which is also implicated in platelet activation and coagulation will also be analyzed. Lastly, with regard to sample size, if our historical projections on numbers of HM2 and HM3, or VA ECMO and Impella fall short, we can increase recruitment an additional 6-12 months to achieve target enrollment.

**Aim 2: To determine the impact of targeted anti-platelet therapy with sildenafil on changes in PA/A and endothelial function during CF MCS mediated LLH.**

**Design:** Prospective, randomized (1:1), double-blind study investigating the effect of a 15-day treatment with (sildenafil) or matched placebo on PA/A in patients with ongoing LLH on durable CF pump (HM2 and HM3).

**Study Population - Inclusion criteria:** Low Level Hemolysis (LLH) is defined as: abnormally elevated LDH  $\geq$  240 U/L, plasma free hemoglobin  $\geq$  10 g/dL, haptoglobin  $\leq$  100 mg/dL. Outpatients  $\geq$  18 years old with ongoing durable CF pump support (HM2 or HM3), off nitrates and sildenafil, will be eligible to participate in this study. If the radial pulse is palpable manually (pulsatile), then those with a systolic blood pressure (BP)  $<$  100 mmHg, taken by a manual blood pressure cuff, will be excluded. If the radial artery pulse is not palpable (non-pulsatile), then those with a Doppler blood pressure  $<$  80 mmHg will be excluded. In non-pulsatile patients, the BP is taken by a Doppler ultrasound at the brachial artery and is closely correlated to the mean arterial BP. Those patients already on sildenafil or nitrates for clinical indications will also be excluded. In addition, patients with an ongoing infection that may predispose to thrombosis will be excluded as will those unwilling or unable to give written, informed consent.

**Study Protocol:** After obtaining informed consent, baseline demographics and hematologic biomarkers including fasting am PA/A and NO bioavailability measurements (3 tubes [1 tube for platelet aggregometry, 1 tube for exploratory biomarkers including p selectin, CD 40L, GPIIb/IIIa receptor, and 1 tube for NO bioavailability] x 3ml = 9 ml of blood) will be collected. In addition, endothelial function will be assessed by flow mediated dilation of the brachial artery and fingertip temperature changes following a 5 min blood pressure cuff inflation. Patients will be placed, using computerized randomization, into 2 groups to receive the study drug which will be either sildenafil or placebo. More precisely, an enrolled patient will be randomly placed in either the placebo or the sildenafil arm, both of which will be marked as "Study Drug." Neither the patient nor the drug administrator will be aware to which study arm the patient has been designated. Following randomization and if BP is in the acceptable range (see figure 4), 20 mg of the study drug will be administered. Then BP will be recorded every 30 mins for two hours. If BP drop is < 5 mmHg after 2 hours and patient is asymptomatic, they will proceed to take 20 mg of the study drug every 8, starting on day 2 (total 18 doses). Patients will be asked to return to the clinic on day 8 and 20 mg of the study drug will be administered. After 2 hours, which is the time of peak drug concentration, fasting am PA/A and NO bioavailability measurements (3 tubes [1 tube for platelet aggregometry, 1 tube for exploratory biomarkers including p selectin, CD 40L, GPIIb/IIIa receptor, and 1 tube for NO bioavailability] x 3ml = 9 ml of blood) will be collected. In addition, endothelial function will be assessed by flow mediated dilation of the brachial artery and fingertip temperature changes following a 5 min blood pressure cuff inflation. Then the patient will be asked to come back to clinic on the next weekday and if BP is in the acceptable range (see figure 4), 40 mg of the study drug will be administered. If BP remains stable for 2 hours (< 5 mmHg drop and asymptomatic), then patients will continue taking 40 mg every 8 hours. Patients will be asked to return to clinic on day 15. A final 40 mg dose of the study drug will be given and after 2 hours fasting am PA/A and NO bioavailability measurements (3 tubes [1 tube for platelet aggregometry, 1 tube for exploratory biomarkers including p selectin, CD 40L, GPIIb/IIIa receptor, and 1 tube for NO bioavailability] x 3ml = 9 ml of blood) will be collected. In addition, endothelial function will be assessed by flow mediated dilation of the brachial artery and fingertip temperature changes following a 5 min blood pressure cuff inflation. All patients will be on a standard antithrombotic regimen of aspirin 81 mg daily with a target INR of 2-2.5 IU.

Endothelial Function Testing will be conducted by non-invasive methodology. As has been previously well described [32], a vascular ultrasound probe will be used to assess the diameter of the brachial artery at the level of the antecubital fossa in the longitudinal view. Then an arm blood pressure cuff will be inflated beyond the systolic pressure for 5 minutes to cause transient ischemia. After deflation of the arm blood pressure cuff, the brachial artery diameter will be recorded again by the ultrasound vascular probe. In addition, by using the noninvasive Endothelix device, we will simultaneously also record figure tip temperature change before and after cuff deflation, as another measure of endothelial function.

Addendum to study protocol:

Aim 2 of this protocol is a randomized, blinded, placebo-controlled study to assess the effect of sildenafil on platelet function in patients supported by left ventricular assist devices. We originally proposed to enroll 46 patients into this study. At this point, 20 participants have successfully completed the study since enrollment which was initiated in 2019. Due to slower than expected enrollment for a variety of reasons, including the COVID-19 pandemic, a competing trial and a reduction in institutional implantation volume of these devices, it is no longer feasible to reach the originally proposed sample size within the planned study period

ending December 30, 2023.

In discussion with my mentoring team, we propose to amend the study protocol to perform an interim analysis at the current sample size of 20 participants. The statistical plan will be carried out as originally proposed in the study plan. If there is a trend at a  $p<0.2$  for a change in platelet function between groups, then we will readjust the required sample size accordingly for the duration of the enrollment period. If this trend is not apparent, then it would be futile to enroll additional patients into this study aim and further enrollment will stop. In this scenario, we will proceed with analysis of proposed study measures with subsequent reporting of findings.

**Statistical analysis, sample size calculations:** The primary measure of PA/A is the change in ADP-induced AUC assessed by platelet aggregometry, which will be compared between the treatment and placebo groups by an independent samples Student's t test. The null hypothesis is that the mean change in PA/A will be the same in both groups at the 15 day time-point. In a prior single-arm study in patients with ongoing hemolysis from SCA, sildenafil reduced PA/A by around 40% from  $30.6\%\pm15.2$  to  $17.3\%\pm12.4$  [17]. If this is the true population effect with standard deviation of the sildenafil induced change in PA/A among patients on durable CF pump support and if there is no expected change in the placebo group, we would need 23 patients per group (46 total patients) to achieve **85% power** to detect a significant difference in mean reduction with a two-sided alpha of 0.05. Analysis will be by intention-to-treat. Although the primary analysis will be unadjusted, secondary analyses will apply linear regression models to adjust for age, sex, race/ethnicity, duration of device implant, type of device (HM2 or 3) and adherence. Given the small sample, adjustment will be limited to no more than 2 additional variables at a time. If device differences are observed, sub-group analyses by device will be performed. For secondary outcomes, the above analyses will be repeated at 8 days and also comparisons of changes in p-selectin, activated GP IIb/IIIa receptor and platelet cGMP at 8 and 15 days.

**Plan for recruitment, retention, timeline and check points:** Patients on CF MCS are tracked closely in a centralized electronic medical registry kept by the HF group, which we will continue to leverage as a resource to identify patients. Currently, 52 outpatients identified through our CF MCS patient registry on durable devices with LLH are available for screening and at the current implant rate of 5 durable devices per month, 1 additional patient with LLH becomes available every month. With an estimated 35% ineligibility or withholding consent, 95 patients with LLH will need to be screened to enroll 62 patients. With an additional 25% drop-out rate after enrollment, this will leave 46 patients (23 per group) who will complete the study protocol. Since 52 outpatients with CF pumps and LLH are currently available (which is steady state for our program based on prior 3 years) and taking into account 35% ineligibility or unwillingness to participate at screening, we estimate that 34 patients can be immediately enrolled to get a head start. At the current availability of 1 new LLH patients per month, it will take an additional 42 months to screen and enroll the remaining patients. We will conduct checkpoints every 6 months examining if the anticipated enrollment (table 2) is being achieved. If enrollment is not met by 2 consecutive check points, we may increase recruitment an additional 6-12 months.

**Anticipated results and experimental problems:** We expect that enhancement of NO signaling with Sildenafil in patients with low level hemolysis will lead to a reduction in PA/A. If changes in PA/A are not observed, then exogenous PA/A will be assessed with platelet poor plasma. If PA/A is not affected, then follow-up experiments will have to be designed to identify the LDH and plasma free hemoglobin threshold value at which lower-level hemolysis increases PA/A.

Alternatively, if the expected reduction in PA/A is not observed with sildenafil we may try other pharmacological agents that also enhance NO signaling such as nitrates.

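### Aim 1 assays the frozen cGMP, vWF and ADAMTS13 specimens weekly in runs averaging about 1.5 patients, with no balancing and no run term, which costs precision in the secondary marker comparisons

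*Combined protocol and SAP*

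**What the plan says.** The storage note after item 4 of the Aim 1 Study Procedures states that specimens for platelet cGMP, vWF and ADAMTS13 are "frozen at -80°C and stored for analysis every week in batches during study period".

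The Aim 1 section on statistical analysis, sample size and timeline gives the accrual:
- Durable pumps: "This will leave 50 HM2 and 75 HM3 patients available for analysis". Of these, "approximately 30% of HM2 (n=15) patients and 20% of HM3 (n=15) will have LLH".
- Acute pumps: "45 VA ECMO and 45 Impella will be enrolled and available for analysis", with 15 LLH and 30 no-LLH patients expected on each device. The supply is "6 acute support CF pumps (3 VA ECMO and 3 Impella) implanted every month", with half of those screened excluded.
- Duration: "we estimate it would take 32 months to enroll and analyze the calculated number of patients for all devices".

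The same section compares the potential mediators between LLH and no-LLH patients, for each device and in any pooled analysis. The list includes "cGMP, vWF activity, UL/HMW multimers, ADAMTS 13 activity by unpaired Student's t tests". Adjustment is foreseen for patient characteristics only.

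The plan does not state a run size, a balance of LLH and no-LLH specimens within a run, a common control sample, or a run term.

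**The concern.** Gels, ELISA plates and FRET runs differ from one run to the next, and kit lots change over nearly three years. When the two groups are compared within the same run, that error cancels. When specimens are spread over many small runs and the test ignores run, it stays in the comparison.

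Four of the six mediators are measured this way: cGMP, vWF activity, UL/HMW multimers and ADAMTS13 activity. They carry the mechanistic part of Aim 1, and each device has only 15 LLH patients. Assay noise that better run planning would avoid therefore lowers the chance of seeing a real marker difference.

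**Working it through.** **1. Timeline check.** Each acute device needs 90 screened at 3 implants a month: 90/3 = 30 months. HM3 needs 115 screened with 30 already available: (115 − 30)/3 = 28.3 months. The plan's 32 months, which includes analysis, is consistent with these.

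**2. Average run size.** Patients: 50 + 75 + 45 + 45 = 215. LLH: 4 × 15 = 60. No LLH: 35 + 60 + 30 + 30 = 155. Weeks: 32 × (365.25/12)/7 = 139.1. Average: 215/139.1 = 1.55 patients per weekly run. The serial inpatient draws are three tubes for PA/A only, so they add nothing to these runs.

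**3. How often an LLH specimen has a same-device comparator in its run.** Assuming even, Poisson accrual, the chance is 1 − exp(−n/139.1), where n is the number of no-LLH patients.

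| Comparison | n (no LLH) | Chance |
|---|---|---|
| VA ECMO, Impella (each) | 30 | 19% |
| HM2 | 35 | 22% |
| HM3 | 60 | 35% |
| All devices pooled | 155 | 67% |

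The HM2 figure is a lower bound in practice: 80 HM2 patients must be screened and 95 HM2 outpatients are available at the start. If all 50 HM2 patients entered within 3, 6 or 12 months, the same formula gives 93%, 74% or 49%.

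**4. How much run error stays in the group difference.** Let n1b and n0b be the LLH and no-LLH counts in run b. The run variance is multiplied by the sum over runs of (n1b/n1 − n0b/n0)². Relative to (1/n1 + 1/n0), which is what independent errors would give, the expected share is 1 − 1/W when specimens fall at random over W runs. With W = 139 this is 138/139 = 99%, both per device and pooled. Simulation of the planned t test (4,000 replicates per setting) also gave about 99%, with bias near zero and type I error of 4.5% to 5.7%.

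Sharing a run by chance therefore helps little while run is neither balanced nor modelled. Even with HM2 accrual packed into 13 weekly runs, 12/13 = 92% of the run variance would remain.

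**5. Effect on power.** The documents give neither the run-to-run error nor an expected marker difference, so both are assumed. Let r be the between-run SD divided by the within-run patient SD. The variance rises by the factor 1 + r², and the standardized difference becomes d/√(1 + r²). Power is from the noncentral t distribution, two-sided 0.05, 15 LLH vs 30 no LLH.

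| r | Variance factor | Equivalent of 15 LLH patients | Power, d = 1.0 | Power, d = 1.2 |
|---|---|---|---|---|
| 0 | 1.00 | 15 | 87% | 96% |
| 0.3 | 1.09 | 13.8 | 84% | 94% |
| 0.5 | 1.25 | 12 | 79% | 91% |
| 0.7 | 1.49 | 10.1 | 72% | 86% |

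The 1.2 is borrowed from the aggregometry effect in the plan: (26 − 20)/5. For HM3 (15 vs 60) at d = 1.2, power is 98% without run error and 98%, 96% and 92% at the three values of r.

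**The case against.** The strongest reply is that this is a modest matter. Only secondary mediator analyses are affected, the plan claims no power for them, and the size of the loss depends on assay error that nobody has stated. With small run error and a large effect, the loss is two or three percentage points. Control samples and run layout may also be set out in laboratory procedures outside the protocol. All of this stands and limits the weight of the point. It does not explain why a weekly rule is needed for specimens already held at -80°C.

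A reader might also infer more than the documents support:
- *That the marker comparisons are biased or confounded by run.* If LLH status is unrelated to calendar time, the error is noise that the t test's standard error already reflects. Bias would need the LLH share and the assay to drift together.
- *That LLH and no-LLH specimens are rarely run together at all.* This is true within a device under even accrual. Across devices about two thirds of LLH specimens share a run with some no-LLH specimen, and early HM2 runs may be well mixed.
- *That comparisons of markers between devices are compromised.* None is planned. The four-device ANOVA concerns PA/A, and aggregometry is performed promptly on fresh blood.
- *That a missed difference would be taken as evidence against the NO or vWF pathway.* The Aim 1 section on anticipated results follows a null cGMP or multimer finding with further assays.

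**Conclusion.** The point holds as a cheap improvement to the secondary marker analyses. Weekly runs averaging about 1.5 patients, analysed by t tests that ignore run, leave about 99% of run-to-run variance in the LLH comparison, per device and pooled. That result assumes specimens fall at random over the weekly runs with regard to LLH status.

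For the acute pumps, over the assumed range of assay error, the loss runs from about 3 to 15 percentage points of power at a 1.0 SD difference and from about 2 to 10 points at 1.2 SD. It is smaller for HM3. These figures illustrate the possible cost and are not estimates for this laboratory. The primary comparison of ADP-induced AUC and its stated 90% power are not touched.

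**What to change.** Replace the weekly rule with a few larger runs from -80°C storage. Each run should hold specimens from every device, with LLH and no-LLH specimens in similar proportion within each device, in random position and under coded labels. A run confined to one device should be avoided, because it would tie device to run in the pooled analysis. Include run as a factor in the LLH comparison of cGMP, vWF activity, UL/HMW multimers and ADAMTS13 activity.

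The cost is one sentence in the Study Procedures and one model term. With five balanced runs and no run error, the term itself lowers power at 15 vs 30 and 1.0 SD only from 87.1% to 86.9%, through lost degrees of freedom. The practical downside is longer frozen storage and later marker results.

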## **Research Protocol and Study Procedures**

### **Aim 1: To evaluate LLH-related PA/A during CF MCS.**

**Design:** In a cross-sectional format, we will recruit patients on chronic and acute CF MCS devices. Device-specific comparisons will be made to assess PA/A between those with and without LLH. In secondary analyses, we will also examine association of LLH with potential mediators of PA/A including activated GP IIb/IIIa receptor, p-selectin, platelet cGMP, vWF activity, vWF UL/HMW multimers and ADAMTS13 activity.

**Population:** Patients  $\geq 18$  years old on durable (HM2 and HM3) and acute (VA ECMO and Impella) CF MCS devices will be approached for participation. We will only approach HM3 patients that are commercially implanted and not enrolled in an ongoing clinical trial. Patients receiving sildenafil or nitrates for clinical indications will be excluded. Plasma Free Hemoglobin (PFHb) and Lactate Dehydrogenase (LDH) levels used to categorize patients as LLH (PFHb 10-20 mg/dL and LDH 400-700 U/L on three consecutive clinical measurements within a 14-day period to assure steady state) or no LLH (PFHb  $< 10$  mg/dL and LDH  $< 400$  U/L) are clinically measured daily in inpatients and every 2 weeks in outpatients at our institution.

Adult patients requiring acute CF pump support with veno-arterial (VA) ECMO or the Impella device for cardiogenic shock with an anticipated support time of at least 48 hours will be approached for participation in this study. The capacity to give informed consent will be evaluated by the study team. Patient's capacity will be assessed through the MacArthur

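### Aim 1's rule for pooling devices rests on a 1-way ANOVA with no residual degrees of freedom as worded, and the pooled analyses do not name device as a covariate

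*Combined protocol and SAP*

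**What the plan says.** The relevant text is in the combined protocol and SAP, under Aim 1 (Design; and Statistical analysis, sample size calculations and timeline).

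- Design: "In a cross-sectional format, we will recruit patients on chronic and acute CF MCS devices". The primary analysis is by device: "ADP-induced AUC will be compared between the LLH and no LLH groups with an unpaired Student's t test".
- Recruitment: "we will recruit for both groups until we have enrolled 15 patients in the LLH group for each device". For durable pumps, "the remainder will be in the no LLH group (35 HM2, 60 HM3"); for VA ECMO and Impella, 30 no-LLH patients each.
- Device differences are to be assessed by "conducting a 1-way ANOVA test of the difference PA/A between LLH and no LLH amongst all 4 device groups", with post-hoc comparisons if the result is significant. Then: "Results from devices that do not show heterogeneity will be pooled to assess the association across device type". No significance level is given for this test.
- Confounders in the pooled sample are handled as in the device-specific analysis, whose list is age, sex, body mass index and race/ethnicity. They are adjusted for where appropriate. Device is not on the list.
- Mediators: "In secondary analyses, we will also examine association of LLH with potential mediators of PA/A". These comparisons, by device and pooled, are unpaired t tests with no covariates.

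**The concern.** A 1-way ANOVA needs replicate observations of its response within each group. Here the response is a difference between two sets of patients, so it exists once per device. The daily repeat samples in Aim 1 come only from inpatients with ongoing LLH and supply no within-patient contrast. The only stated rule for pooling therefore cannot be carried out as written, and the analyst would have to choose a replacement, possibly after seeing the data.

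The second part concerns what happens after pooling. Recruiting to a fixed 15 LLH patients per device, with different numbers of no-LLH patients, gives the two groups different device mixes. If PA/A or a mediator differs by device for reasons other than LLH, a pooled comparison without device attributes part of that difference to LLH.

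**Working it through.** **Inputs from Aim 1.** Means 20 and 26 AU with SDs 5 (no LLH) and 4 (LLH); two-sided alpha 0.05. Counts in the order HM2, HM3, VA ECMO, Impella: LLH 15/15/15/15 (total 60), no LLH 35/60/30/30 (total 155). Device shifts in PA/A are my assumptions. Results are given for SDs 4/5 and for an equal SD of √((16+25)/2) = 4.53.

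**1. The plan's own figure.** Power with 15 per group, normal approximation:
- SD 5: 6/(5·√(2/15)) − 1.96 = 3.29 − 1.96 = 1.33, or 90.8% (88.7% by noncentral t).
- SD 4.53: 95.2% (93.8% by noncentral t).

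The stated 90% is reproduced, and nothing below changes it.

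**2. Degrees of freedom.** Test as worded: 4 differences − 4 groups = 0 residual; software returns no F value. Patient-level model with LLH, device and their interaction: N = 50+75+45+45 = 215, with 8 cell means. The interaction has (4−1)(2−1) = 3 df and the residual 215 − 8 = 207.

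**3. Device mix.** Each device is 15/60 = 25% of LLH. Shares of no LLH are 35/155 = 22.6%, 60/155 = 38.7%, and 30/155 = 19.4% twice. The gaps (LLH minus no LLH) are +0.024, −0.137, +0.056 and +0.056. The plan says "at least 35% of patients for each acute CF pump" will have LLH, but 15/45 = 33.3%. With 16/45, the HM3 gap is 15/62 − 60/153 = −0.150, little different.

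**4. Bias of a crude pooled contrast** = Σ(gap × device shift).
- HM3 lower by 4.53 AU: 0.137 × 4.53 = 0.62 AU; by 5 AU: 0.69 AU. This is about a tenth of the planned 6 AU.
- Both acute devices higher by 4.53 AU: 0.113 × 4.53 = 0.51 AU.

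**5. Type I error** with no LLH effect (40,000 simulated trials per row, nominal 5%):

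| Assumed shift | SDs 4/5: crude vs with device | Equal SDs: crude vs with device |
|---|---|---|
| None | 3.1 vs 3.1% | 4.9 vs 4.9% |
| HM3 −4.53 AU (1 SD) | 7.9 vs 3.1% | 10.4 vs 5.1% |
| HM3 −2.27 AU (0.5 SD) | 4.4 vs 3.1% | 6.5 vs 5.0% |
| Both acute +4.53 to +5 AU | 5.6-5.7 vs 3.0-3.2% | 7.6-8.0 vs 4.8-5.1% |
| HM2 −5 AU | 2.2 vs 3.2% | 3.4 vs 5.1% |
| VA ECMO −5 AU | 3.0 vs 3.1% | 4.7 vs 5.0% |

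Allowing for repeat runs and a shift of up to 5 AU, the 1 SD HM3 case lies at about 7-11% crude. The 3% values arise because the larger group has the larger SD, which makes pooled-variance tests conservative.

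**6. What the interaction test can detect.** If the effect is 3 AU in one device and 6 AU in the others, power is 22-26% (SDs 4/5) or 30-33% (equal SDs). With SDs 4/5 the ordinary F test rejects in only about 2.4% of null trials.

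**7. Precision of device-specific effects.** Half-width of the 95% CI from the linear model = 1.971 × s × √(1/15 + 1/n of no LLH).
- SDs 4/5: s = √((56×16 + 151×25)/207) = 4.75, giving 2.70 (HM3) to 2.96 AU (acute devices).
- Equal SDs: 2.58 to 2.82 AU.
- Separate variances and 1.96: 1.96·√(16/15 + 25/n) = 2.39 to 2.70 AU.

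**8. Cost of keeping device.** With w = 1/(1/15 + 1/n of no LLH) = 10.5, 12, 10, 10 (sum 42.5), the standard-error ratio is √(1/42.5)/√(1/60 + 1/155) = 0.1534/0.1520 = 1.009.

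**The case against.** The strongest reply is that the sentence names its target, the LLH contrast compared across devices, so a competent analyst would fit the interaction. That stands as a reading of intent, and it limits the point to a specification gap.

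A reader might go further and infer that the choice of substitute makes the pooling decision arbitrary, since an ANOVA of mean PA/A by device disagrees with the interaction test in 92-98% of simulated trials when device means differ and LLH effects do not. The documents do not support that inference. The mean-by-device ANOVA tests a different null hypothesis from the one the sentence names, so the disagreement is built in. A heterogeneity test of the four differences using their own standard errors keeps the stated target. It disagreed with the interaction test in only 2.4-6.5% of trials in the scenarios compared (no heterogeneity, HM3 shifted, no effect in VA ECMO).

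Nor should the two problems be added together for pooled PA/A. If mean PA/A by device were used to decide pooling, a 1 SD HM3 shift would be flagged almost always, and a false-positive crude pooled result occurred in 0.0% of null trials (0.8-0.9% at 0.5 SD). The inflated type I error needs the interaction reading together with omission of device.

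It is also fair that the plan already has a post-hoc step, and that its general provision on confounders could admit device for pooled PA/A. That provision does not reach the pooled mediator t tests, which have no place for a covariate and whose pooling depends only on the PA/A result.

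**Conclusion.** The point holds as a minor item for secondary analyses. Two parts need no assumption: the heterogeneity test as worded has zero residual degrees of freedom, and device is not named in any pooled analysis although the device mix differs by plan.

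The size of the confounding does rest on assumption. It matters modestly if HM3 differs by a full SD or both acute devices do, hardly at 0.5 SD in HM3 (4.4-6.6%), and causes no inflation of type I error if HM2 or VA ECMO alone is shifted. It bears mainly on the mediator comparisons.

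A reader might infer that Aim 1 cannot assess device heterogeneity, or that its main result is compromised. Neither follows. The patient-level data support the interaction test, and the device-specific primary t tests and their 90% power do not depend on pooling.

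**What to change.** In Aim 1's statistical analysis section:

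1. Replace the ANOVA sentence with a linear model for PA/A containing LLH, device and LLH × device. Use the 3-df interaction test as the criterion for pooling and state its significance level. Make it robust to unequal variances, since the ordinary F test is conservative with SDs 4/5. State that a comparison of mean PA/A by device does not decide pooling.
2. Base the existing post-hoc step on pairwise interaction contrasts, so that it is clear which devices may be pooled after a significant result.
3. Report the LLH effect and 95% CI for each device whatever the test shows. With power of only about 22-33% when the effect is halved in one device, a non-significant result is weak evidence of homogeneity.
4. Keep device in every pooled PA/A and mediator model, replacing the pooled mediator t tests.

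This needs no new data. The cost is SAP wording, three degrees of freedom among 215 patients, and about 0.9% more standard error for the pooled LLH effect.
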